6.9. Subject Withdrawal/Early Termination

Subjects may withdraw from the study at any time at their own request, or they may be withdrawn at any time at the discretion of the investigator or Sponsor for safety or behavioral reasons, or the inability of the subject to comply with the protocol required schedule of study visits or procedures at a given study site.

If a subject cannot be contacted within the window for a scheduled visit, every effort should be made to contact the subject outside of the visit window. A subject thought lost to follow-up, must be contacted through a minimum of 3 documented phone call attempts and, if phone calls are unsuccessful, a certified letter sent to the subject. All attempts to contact the subject and information received during the contact attempts must be documented in the subject's medical records. In any circumstance, every effort should be made to document the subject's outcome, if possible. The investigator should inquire about the reason for withdrawal, request that the subject return for a final visit, if applicable, and follow-up with the subject regarding any unresolved adverse events (AEs).

If the subject is willing, the investigator should query for any new adverse events, query about concomitant analgesic medication use, physical rehabilitation activities or corrective procedures related to the joint replacement surgery and request that the subject complete the following assessments via the IWRS or via paper, as established at the Baseline Visit:

- Pain in Replaced Joint (11-point NRS).
- Functional status (WOMAC for subjects with a total knee or hip replacement or SPADI for subjects with a total shoulder replacement) (WOMAC or SPADI).

- Overall satisfaction with joint replacement surgery (SAPS).

Subjects not utilizing the IWRS should be reminded to return paper based assessments to the site as soon as possible, but no later than 5 days, after completion of the assessment.

If the subject withdraws from the study, and also withdraws consent for disclosure of future information, no further evaluations should be performed, and no additional data should be collected. The sponsor may retain and continue to use any data collected before such withdrawal of consent.

7. ASSESSMENTS

Every effort should be made to ensure that the protocol required procedures are completed as described. However it is anticipated that from time to time there may be circumstances, outside of the control of the investigator, that may make it unfeasible to perform a procedure. In these cases the investigator will take all steps necessary to ensure the safety and well-being of the subject. When a protocol required procedure cannot be performed the investigator will document the reason for this and any corrective and preventive actions that he or she has taken to ensure that normal processes are adhered to as soon as possible. The study team will be informed of these incidents in a timely fashion.

7.1. Surgeon's Assessment of Procedural Difficulty

Following the total joint replacement surgery, the orthopedic surgeon performing the surgery will be asked to answer the following question:

“Taking into consideration the subject's medical history and physical condition prior to surgery would you classify the operative procedure as:

1. Uneventful; or
2. Minor complications; or
3. Major complications.

If the category of minor or major complications is chosen, the surgeon will be requested to specify the complication(s).

7.2. Pathology Specimens

Surgeons will be requested to ship pathology specimens from the total joint replacement surgery to a central laboratory for processing and/or analysis. Detailed instructions for the shipping of pathology specimens will be provided. Identification of specimens of adequate quality, preparation and histopathologic examination of the specimens will be performed in a standardized manner by the central laboratory under the direction of an expert orthopedic pathologist.

7.3. Telephone-based Assessments

Post-surgery, subjects will be contacted monthly via telephone by study site personnel.

7.3.1. Adverse Events

At each post-surgery telephone contact, subjects will be queried for the occurrence of adverse events. All adverse events reported by the subject must be recorded on the appropriate case report form (CRF).

A neurologic evaluation should be performed by a consulting neurologist if any of the following occurs:

- If an adverse event suggestive of new or worsening peripheral neuropathy or an adverse event of abnormal peripheral sensation (eg, allodynia, burning sensation, carpal tunnel syndrome, dysesthesia, hyperesthesia, hyperpathia, hypoesthesia, neuralgia, neuritis, neuropathy peripheral, pallesthesia, paresthesia, peripheral sensory neuropathy, sciatica, sensory disturbance, sensory loss, tarsal tunnel syndrome) is reported as: 1) a serious adverse event or 2) an adverse event which has resulted in the subject being withdrawn from the study, or 3) an adverse event ongoing at the end of the subject's participation in the study, or 4) an adverse event of severe intensity.
- A neurological adverse event which is non-neuropathic (eg, stroke, seizure) but which the investigator considers medically important should also result in a neurological consultation.

In these cases, a neurologic evaluation should be obtained as soon as possible after these signs and symptoms are known. The results of the neurological consultation will be recorded on the appropriate CRF and adverse event (if applicable) forms. Adverse events will be reported where applicable as described in [Section 8](#).

Subjects reporting adverse events (any seriousness or severity) with preferred terms of bradycardia, syncope, orthostatic hypotension, anhidrosis or hypohidrosis should be further evaluated for the presence of sympathetic autonomic neuropathy by a cardiologist or neurologist as soon as possible.

The investigator should determine the appropriate type of consultation (neurology or cardiology) depending on the subject's symptom presentation and the investigator's assessment as to the specialist best able to evaluate the subject. Pfizer will provide a guidance document which outlines appropriate recommendations regarding tests to consider for subject work-up.

7.3.2. Concomitant Analgesic Medication

At each post-surgery telephone contact, subjects will be queried about concomitant analgesic medication usage including dose, dosing regimen and reason for use. This information should be recorded on the appropriate case report form (CRF).

7.3.3. Physical Rehabilitation Activities

At the Week 4, 12 and 24 post-surgery telephone contacts, subjects will be queried for rehabilitation activities related to the replaced joint. Specifically, subjects will be asked to respond yes or no to the following question:

- Are you participating in physical rehabilitation activities related to your replaced joint?

Subjects will be queried for details if the answer to the question is yes. This information should be recorded on the appropriate case report form (CRF).

7.3.4. Additional or Corrective Procedures

At the Week 12 and 24 post-surgery telephone contacts, subjects will be queried for additional or corrective procedures related to the total joint replacement surgery. Specifically, subjects will be asked to respond yes or no to the following question:

- Have you been told by your orthopedic surgeon that additional or corrective procedures (for example a revision or implant replacement) are necessary for your total joint replacement?

Subjects will be queried for details if the answer to the question is yes. If necessary, the orthopedic surgeon may be contacted to confirm/expand upon the information regarding additional or corrective procedures. This information should be recorded on the appropriate case report form (CRF).

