2.3. Endpoints

Given the design of this study, the following endpoints are considered co-equal:

- Surgeon's Assessment of Procedural Difficulty: number and percentage of surgeries assessed as uneventful, minor complications or major complications.
- Subject's overall satisfaction with surgery as assessed by the Self-Administered Patient Satisfaction (SAPS) Scale: number and percentage of subjects satisfied vs. unsatisfied with their total joint replacement at Week 24.

- Number and percentage of subjects with a post-surgical complication(s) up to Week 24 (derived from reported adverse events; see also [Section 9](#)).
- Number and percentage of subjects with additional or corrective procedures related to their total joint replacement up to Week 24.
- Number and percentage of subjects participating in physical rehabilitation activities related to the replaced joint up to Week 24.
- Change from Baseline to Week 24 in average pain in the replaced joint.
- Change from Baseline to Week 24 in WOMAC Pain, Stiffness and Physical Function subscales in the replaced joint (subjects undergoing total hip or knee replacement surgery only).
- Change from Baseline to Week 24 in the SPADI in the replaced shoulder (subjects undergoing total shoulder replacement surgery only).
- Concomitant analgesic medication use.

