3. STUDY DESIGN

This is a Phase 3, multicenter, long-term observational study of subjects from tanezumab Study A4091056, A4091057 or A4091058 (regardless of treatment group) who undergo a total knee, hip or shoulder replacement during participation in the study (treatment period or safety follow-up period). If while the subject is participating in this study (A4091064), the subject undergoes an additional total joint replacement surgery or the site becomes aware that an additional total joint replacement surgery has been scheduled for the subject, the subject will be requested to provide information on the additional total joint replacement surgery as well. Finally, any subject with a qualifying total joint replacement after the last subject in the study completes the treatment period in studies A4091059, A4091061 or A4091063 may be followed in this study (A4091064).

This study is designed with a total duration of subject follow-up of 24 weeks after the total joint replacement surgery. There will be two methods of data collection utilized in this study: interview by site staff via the telephone and IWRS accessed by desktop, laptop or tablet computer (or paper if the subject has no access to the internet via a desktop, laptop or tablet computer). Following the surgery, the subject will be contacted monthly via telephone by study site personnel to ascertain whether the subject has experienced any adverse events and to record any concomitant analgesic medications the subject is taking as well as the reason for the medication use. An assessment of the subject's overall satisfaction with their total joint replacement (IWRS), average pain in the replaced joint (IWRS), the subject's level of function and activity in the replaced joint (IWRS) and physical rehabilitation activities (telephone interview) will be made at Weeks 4, 12 and 24. At Weeks 12 and 24, subjects will be queried during the telephone interview as to whether any additional or corrective procedures related to the total joint replacement are planned.

Any subject who expresses a desire to leave this study before 24 weeks of follow-up have been completed should be asked to complete all assessments scheduled for Week 24.

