At the Week 4, 12 and 24 post-surgery telephone contacts, subjects will be queried for rehabilitation activities related to the replaced joint. Specifically, subjects will be asked to respond yes or no to the following question:

- *Are you participating in physical rehabilitation activities related to your replaced joint?*

Subjects will be queried for details if the answer to the question is yes.

The data relating to the endpoints of physical rehabilitation, or additional or corrective procedure, related to the replaced joint up to Week 24 will be derived from an ongoing clinical review of the concomitant non-drug treatment/procedure case report form (CRF) page. This review will identify treatments that are relevant for these endpoints, and a log of such data will be maintained. The data relating to the endpoint of concomitant analgesic medication use will be derived from an ongoing review of the concomitant analgesic drug CRF page. These reviews will be made during the study and data will be finalized prior to the database release for this study.

Events identified as the first symptom leading to total joint replacement will be reviewed and determined prior to the unblinding for the respective parent study.

The list of post-surgical complications will be derived from reported adverse events and will consist of complications that are clinically significant and attributable to the total arthroplasty procedure eg, periprosthetic joint infection/wound infection, periprosthetic fracture, pulmonary embolism or sepsis/septicemia/shock. The list of post-surgical complications will be developed during Study A4091064 and finalized prior to Study A4091058 unblinding. Other adverse events may be identified as post-surgical complications after the unblinding of the Study A4091058 database. These events will also be summarized as complications, and will be noted as having been included in the list after the unblinding of the Study A4091058 database.

Adverse Events which are “treatment emergent” in relation to the Baseline study day will be reported overall and by prior study treatment group. Adverse events ongoing from the parent study will continue to be followed in this study. They will not be included in incidence tables from this study unless the severity worsens.

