For the subject's overall satisfaction with surgery assessments (using the Self-Administered Patient Satisfaction scale, SAPS), the responses [score] for each category (Very Satisfied [100], Somewhat Satisfied [75], Somewhat Dissatisfied [50], Very Dissatisfied [25]) will be stratified by surgery type (hip, knee or shoulder) and summarized for each of the four items. The scale score is the unweighted mean of the scores from the individual items, ranging from 25 to 100 per item with higher scores indicating greater satisfaction. This total score (mean of the 4 items) will be summarized by surgery type (hip, knee or shoulder) and overall. Responses to the question "How satisfied are you with the results of your surgery?" will also be stratified by surgery type (hip, knee or shoulder) and summarized as satisfied (very satisfied and somewhat satisfied categories combined) and dissatisfied (somewhat dissatisfied and very dissatisfied categories combined).

The total satisfaction score will be summarized using the mean (with standard deviation), median, and minimum and maximum values. These results will be shown by visit, with Week 24 (LOCF).

Similarly, the number and percentage of subjects who have required (i) additional or corrective procedures related to their total joint replacement and (ii) participating in physical rehabilitation activities related to their replaced joint will be presented. For this assessment, change from Baseline summary data are not relevant and will not be presented. This summary will be shown separately for total joint replacements of the hip, knee and shoulder, as well as shown overall. These summaries will be shown for any post-surgery timepoint. Average pain (NRS) in the replaced joint for all subjects, WOMAC Pain, Stiffness and Physical Function sub-scale scores for subjects who had total knee or hip replacement and SPADI Pain, Function and Total Score for subjects who had total shoulder replacement will be summarized (including change from Baseline summaries).

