4.1 Unblinded at or after Database Release

Following database release for phase 3 parent studies, unblinding of each parent study (and sub-studies) will occur at the individual subject level as well as at the summary (ie, treatment group) level to the A4091064 team members who are NOT defined as colleagues who remain blind in the section 4.2.

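### The SAP does not say how a subject who is told a corrective procedure is necessary, but has not yet had it, is counted, and the review that decides is not tied to parent-study unblinding

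*Protocol*

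**What the plan says.** The event is worded in several ways:

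- **Endpoint** (Protocol 2.3, repeated in SAP 6.1): "Number and percentage of subjects with additional or corrective procedures related to their total joint replacement up to Week 24".
- **Design** (Protocol 3, repeated in SAP 2.1): subjects are asked at Weeks 12 and 24 "whether any additional or corrective procedures related to the total joint replacement are planned".
- **Question put to the subject** (Protocol 7.3.4, repeated in SAP 6.1): "Have you been told by your orthopedic surgeon that additional or corrective procedures (for example a revision or implant replacement) are necessary". A yes leads to a request for details, and the surgeon may be contacted. The information goes on a CRF that is not named.
- **Analysis** (Protocol 9.2 and SAP 8.2.1): "the number and percentage of subjects who have required (i) additional or corrective procedures related to their total joint replacement".
- **Data source** (SAP 6.1): the data for this endpoint and for physical rehabilitation "will be derived from an ongoing clinical review of the concomitant non-drug treatment/procedure case report form (CRF) page". The review picks out the relevant treatments and keeps a log, to be final before this study's database release.

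SAP 8.2.2 adds only that the summary covers any time after surgery and uses observed data.

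On blinding, Appendix 2 section 4.1 of the SAP states that after database release "unblinding of each parent study (and sub-studies) will occur at the individual subject level" to team members who are not in the roles listed in its section 4.2.

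**The concern.** The study exists because of a concern that subjects treated with tanezumab may have a different post-surgical outcome (Protocol 1.2.4). A replaced joint that needs revision is a direct sign of that, and this endpoint is one of the co-equal set.

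Two things are left open. First, the question records advice, while the SAP takes the data from a page reviewed for treatments. A subject told at the Week 24 call that a revision is needed later has answered yes and has arguably required a procedure, but may have no performed procedure to log. The adverse event tables need not recover the case, because Protocol 8.7 says that surgery is not itself reported as an adverse event.

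Second, deciding which entries are relevant is a judgement. If it is made with knowledge of the parent treatment, it can introduce bias between groups into the comparison with NSAID that is a secondary objective.

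**Working it through.** The documents state no expected rate, sample size formula or power for this endpoint, so there is no figure of the plan's own to reproduce. The check is a comparison of texts, then an illustration on assumed rates.

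**1. How each wording classifies three subjects**

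| Subject | Question (told necessary) | Analysis text (required) | Endpoint (with a procedure up to Week 24) | SAP review of the CRF page |
|---|---|---|---|---|
| Revision performed at Week 20 | Yes, if reported at the call | Yes | Yes | Yes, if logged |
| Revision advised at Week 22, scheduled after Week 24 | Yes | Arguably yes | On a plain reading, no | Not stated |
| Told necessary at Week 12, later corrected by the surgeon | Yes at Week 12 | Arguably no | No | Not stated |

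The second subject is the critical one. Two wordings tend to include the case, one tends to exclude it, and the derivation rule is silent. Neither document says that a yes alone is an event, or that an advised procedure must be entered on the reviewed page.

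**2. When each judgement must be final**

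| Judgement | Deadline in SAP 6.1 | Later changes |
|---|---|---|
| First symptom leading to joint replacement | Before unblinding of the respective parent study | None provided for |
| List of post-surgical complications | Before A4091058 unblinding | Allowed, and noted as added after unblinding |
| Corrective procedures and rehabilitation (CRF-page review) | Before database release of this study | No flag |

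Only the third is not tied to parent-study unblinding. Appendix 2 section 2 of the SAP defends the unblinding of team members partly on the ground that major endpoints come from patients or surgeons and are not evaluated by an investigator or the sponsor's study team. A clinical review that selects relevant entries does not sit easily with that ground. Protocol 5 also says that sponsor staff directly involved with this study will be blinded to the parent treatment.

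**3. Illustration of size (assumed rates)**

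Inputs: N = 250, the ceiling from Protocol 9.1, where fewer than 250 are expected; q = share told by Week 24 that a procedure is necessary, assumed 2% to 6%; f = share of those not performed or not logged by Week 24, assumed 0% to 50%.

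Formulas: number missed = N × q × f; reported rate = q × (1 − f); chance that at least one is missed = 1 − (1 − q × f)^N.

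| q | f | Yes subjects | Missed | Reported rate | Chance of at least one missed |
|---|---|---|---|---|---|
| 2% | 0% | 5 | 0 | 2.0% | 0 |
| 2% | 25% | 5 | 1.25 | 1.5% | 0.714 |
| 2% | 50% | 5 | 2.5 | 1.0% | 0.919 |
| 4% | 0% | 10 | 0 | 4.0% | 0 |
| 4% | 25% | 10 | 2.5 | 3.0% | 0.919 |
| 4% | 50% | 10 | 5 | 2.0% | 0.994 |
| 6% | 0% | 15 | 0 | 6.0% | 0 |
| 6% | 25% | 15 | 3.75 | 4.5% | 0.977 |
| 6% | 50% | 15 | 7.5 | 3.0% | 1.0 |

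For example, with q = 4% and f = 25%, missed = 250 × 0.04 × 0.25 = 2.5, and the reported rate is 4% × 0.75 = 3.0%.

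For one group of 83, about a third of 250 and again an assumption because the split is unknown, the same ranges give 0 to 2.49 missed of 1.66 to 4.98 yes subjects. Every range starts at zero: if the page already holds advised procedures, f = 0 and nothing is lost.

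**The case against.** The strongest reply is that the loss depends on a form that the documents do not show. The answer, its details and any surgeon confirmation go on an unnamed CRF, and SAP 6.1 repeats the question shortly before naming the procedures page. That page may be where the answers are recorded, and nothing says that it excludes advised procedures. Moreover, the endpoint as defined covers procedures up to Week 24, so leaving out one that takes place later need not be an undercount. Both points stand. A reader might infer that failed replacements will be undercounted; the text supports only that they may be.

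A reader might also infer that a standard subject answer has been replaced by a judgement. The protocol never makes the bare answer the endpoint, and it allows the surgeon to confirm or expand on it. The review can also pick up procedures in subjects who miss a call.

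Nor do the documents show that the reviewers will be unblinded. The review is ongoing during the study. Appendix 2 section 4.2 keeps several roles blinded, including the sponsor clinician who deals directly with sites on joint replacement evaluation, and site staff. The reviewers are not identified and may be among them. What remains is that nothing requires it.

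Finally, some failing joints will appear as post-surgical complications, which SAP 8.2.1 draws from adverse events and non-drug procedures. That is partial cover, because not every advised revision has a reportable event behind it.

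**Conclusion.** The point holds as a gap in definition and in protection against bias. The plan asks about necessity and analyses requirement, but derives the endpoint from a review with no rule for advice without performance. That review has a weaker safeguard than the two comparable judgements in the same SAP section.

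The size is unknown. On assumed rates at the 250 ceiling it runs from no missed subjects to 7.5 of 15. The analysis is descriptive, so no error rate or power is affected. The effect is on the reported percentage, which in a descriptive study is the result itself, and with so few expected events two or three subjects change it visibly.

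The conclusion rests on two things that the documents leave open: what the procedures page collects, and who carries out the review. A reader might extend the point to an undercount of rehabilitation, which shares the data source. The documents do not support that. The rehabilitation question is in the present tense at Weeks 4, 12 and 24, so a review covering any time after surgery can find activity between calls that the answers alone would miss.

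**What to change.** In SAP 6.1 and 8.2.1, report by parent treatment group:

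- (a) any yes to the protocol question at Week 12, Week 24 or early termination;
- (b) procedures performed up to Week 24, from the CRF-page review;
- (c) either (a) or (b).

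Note any answer later corrected by the surgeon, and state which row is the Protocol 2.3 endpoint.

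Require the CRF-page review for the corrective-procedure and rehabilitation endpoints to be done by people blinded to parent treatment. Alternatively, finalize it before parent-study unblinding and flag later additions, as is already done for complications. For rehabilitation, count a yes answer or a relevant CRF-page entry.

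The cost is SAP wording and two extra table rows. The question is already asked at the scheduled calls and at early termination (Protocol 6.9), so no new contact with subjects is needed.
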